## 2. Other variables

Demographics: Age, race, gender, insurance status, medical history (depression, stroke, TIA, DM, CAD, AF, HF, HTN, PVD, smoking)

Presentation variables: EMS transport, ambulatory status, initial NIHSS, prior antidepressant use

In-hospital variables: Dysphagia screening, DVT prophylaxis, t-PA, t-PA date/time, VTE interventions, documented DVT/PE, antithrombotics by day 2

Discharge variables: Discharge disposition, ambulatory status at discharge, ICD-9 discharge diagnosis, Antiplatelet/anticoagulant/HTN/AD meds, stroke education, smoking cessation, assessment for rehabilitation services

Hospital variables: Primary stroke center; comprehensive stroke center, teaching status, hospital bed size, rural location, region, annual volume of IS admissions

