### 3. Outcomes/Endpoints

#### Primary:

- Home-time: Total number of days spent alive and outside of a hospital, skilled nursing facility, or inpatient rehabilitation facility since discharge

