Hospital characteristics				
Teaching status				
Rural location				
Region				
Primary Stroke Centers				
Comprehensive Stroke Centers				
Hospital size, mean (SD)				
Annual IS admission volume, mean (SD)				

All numbers presented are proportions of patient in the study population, unless specified otherwise.

\* P-values from chi-squared tests for independence for categorical variables and Wilcoxon rank sum tests for continuous variables

## 2. Objective 2

**Aim:** To estimate the associations between antidepressant use (any vs. none) and outcomes (home time, all-cause mortality, all-cause readmission recurrent stroke [ischemic, hemorrhagic], cardiovascular rehospitalization, and depression-related hospitalization [suicidality or major depressive episode] following discharge).

**Analysis:** Because patients who receive AD may differ from those who do not on important baseline and clinical characteristics that may affect the likelihood of adverse events, we will use inverse probability of treatment weighting (IPW) when assessing treatment effects. IPT weighting will be accomplished in two steps: First, we will use a logistic regression model to assign a probability of treatment selection to each patient based on the distribution of a defined set of covariates (listed above). The binary outcome for the selection model will be AD treatment (Y/N). In the second step, we will weight subject by the inverse of this assigned treatment probability, resulting in a pseudo-randomization of patients to AD vs. no AD treatment. The distribution of baseline patient characteristics for each treatment group will be assessed after weighting to determine adequacy of the selection model.

Following IPW, we will compare primary and secondary endpoints between treatment groups. Unadjusted rates of all-cause mortality, all-cause readmission, CV readmission, depression-related admission and stroke/TIA readmission will be examined using a Cox proportional hazards model with AD use as the single independent variable. Adjusted event rates will then be estimated using the same model with IPW included for each subject. Within-hospital clustering will be accounted for using robust estimator approach.

Home time will be examined first as a continuous variable in a linear regression model and then as a dichotomous outcome in an IPW-weighted logistic regression model, using 100% of time spent at home over 1 year as the primary outcome of interest.

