Variables	SSRI at Discharge	Other AD at Discharge	StdDiff, %	P-value*
Demographics				
Age, year, mean (SD)				
Gender: Female				
Race/Ethnicity				
Medical History				
Depression				
Atrial Fibrillation				
Stroke/TIA				
CAD/MI				
Carotid Stenosis				
Diabetes Mellitus				
PVD				
Hypertension				
Smoker				
Dyslipidemia				
Heart Failure				
Medications prior to admission				
Antidepressants				
Anti-hypertensives				
Cholesterol-reducers				
Diabetic medications				
Presentation				
EMS transport				
Initial NIHSS				
Onset to arrival times (Prehospital delay)				
<2 hours				
2-4 hours				
>4 hours				
Symptoms resolved at time of presentation				
Ambulatory status on admission				
Labs				
Body Mass Index, mean (SD)				
Systolic blood pressure, mean (SD)				
Hemoglobin A1C, mean (SD)				
LDL-C, mean (SD)				
Hospital characteristics				
Teaching status				
Rural location				
Region				
Primary Stroke Centers				
Comprehensive Stroke Centers				
Hospital size, mean (SD)				
Annual IS admission volume, mean (SD)				

## 6. Objective 6

**Aim:** To estimate the associations between antidepressant use (any vs. none) and patient reported outcomes (modified Rankin Scale, EQ-5D-3L Health Profile, PHQ-2 score, SIS-16 score and Fatigue Severity Scale score).

**Figure 6.** Grotta bar showing AD vs no AD use and mRS following ischemic stroke discharge.

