## EQ-5D-3L Health Profile

Table 6A. EQ-5D-3L distribution by AD use at discharge, 3 month and 6 month

EQ-5D-3L Dimension		AD (% Subjects)			Not on AD (% Subjects)		
		At discharge	3 month	6 month	At discharge	3 month	6 month
Mobility	Level 1						
	Level 2						
	Level 3						
Self-Care	Level 1						
	Level 2						
	Level 3						
Usual Activity	Level 1						
	Level 2						

	Level 3						
Pain/Discomfort	Level 1						
	Level 2						
	Level 3						
Anxiety/Depression	Level 1						
	Level 2						
	Level 3						

Table 6B. EQ-5D-3L index values

EQ-5D-3L index value	AD			Not on AD		
	At discharge	3 month	6 month	At discharge	3 month	6 month
Mean (Standard error)						
Median (25 th – 75 th percentile)						

Table 6C. EQ VAS

EQ VAS	AD			Not on AD		
	At discharge	3 month	6 month	At discharge	3 month	6 month
Mean (Standard error)						
Median (25 th – 75 th percentile)						

Table 6D. PHQ-2 Score distribution

PHQ-2 Score	AD (% Subjects)			Not on AD (% Subjects)		
	At discharge	3 month	6 month	At discharge	3 month	6 month
0						
1						
2						
3						
4						
5						
6						

Table 6E. PHQ-2 Score

PHQ-2 Score	AD			Not on AD		
	At discharge	3 month	6 month	At discharge	3 month	6 month
Mean (Standard error)						
Median (25 th – 75 th percentile)						
% Subjects >= 3						

Table 6F. Stroke Impact Scale-16

SIS-16	AD			Not on AD		
	At discharge	3 month	6 month	At discharge	3 month	6 month
Mean (Standard error)						
Median (25 – 75 percentile)						
Percent at floor (SIS16 = 0)						
Percent at Ceiling (SIS16 = 100)						

[figure not shown]
Table 6G. Fatigue Severity Scale

Fatigue Severity Scale	AD			Not on AD		
	At discharge	3 month	6 month	At discharge	3 month	6 month
Mean (Standard error)						
Median (25 th – 75 th percentile)						
% Subjects >= 36						

## 7. Objective 7

**Aim:** To estimate the associations between antidepressant use (SSRI vs. other) and patient reported outcomes (modified Rankin Scale, EQ-5D-3L Health Profile, PHQ-2 score, SIS-16 score and Fatigue Severity Scale score).

**Figure 7.** Grotta bar showing SSRI vs other AD use and mRS following ischemic stroke discharge.

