## EQ-5D-3L Health Profile

Table 7A. EQ-5D-3L distribution by AD type use at discharge, 3 month and 6 month

EQ-5D-3L Dimension		SSRI (% Subjects)			Other type AD (% Subjects)		
		At discharge	3 month	6 month	At discharge	3 month	6 month
Mobility	Level 1						
	Level 2						
	Level 3						
Self-Care	Level 1						
	Level 2						
	Level 3						
Usual Activity	Level 1						
	Level 2						
	Level 3						
Pain/Discomfort	Level 1						

	Level 2						
	Level 3						
Anxiety/Depression	Level 1						
	Level 2						
	Level 3						

Table 7B. EQ-5D-3L index values

EQ-5D-3L index value	SSRI			Other AD		
	At discharge	3 month	6 month	At discharge	3 month	6 month
Mean (Standard error)						
Median (25 th – 75 th percentile)						

Table 7C. EQ VAS

EQ VAS	SSRI			Other AD		
	At discharge	3 month	6 month	At discharge	3 month	6 month
Mean (Standard error)						
Median (25 th – 75 th percentile)						

Table 7D. PHQ-2 Score distribution

PHQ-2 Score	SSRI (% Subjects)			Other AD (% Subjects)		
	At discharge	3 month	6 month	At discharge	3 month	6 month
0						
1						
2						
3						
4						
5						
6						

Table 7E. PHQ-2 Score

PHQ-2 Score	SSRI			Other AD		
	At discharge	3 month	6 month	At discharge	3 month	6 month
Mean (Standard error)						
Median (25 th – 75 th percentile)						
% Subjects >= 3						

Table 7F. Stroke Impact Scale-16

SIS-16	SSRI			Other AD		
	At discharge	3 month	6 month	At discharge	3 month	6 month
Mean (Standard error)						
Median (25 – 75 percentile)						
Percent at floor (SIS16 = 0)						
Percent at Ceiling (SIS16 = 100)						

Table 7G. Fatigue Severity Scale

Fatigue Severity Scale	SSRI			Other AD		
	At discharge	3 month	6 month	At discharge	3 month	6 month
Mean (Standard error)						
Median (25 th – 75 th percentile)						
% Subjects >= 36

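### SAP Objective 6 aims to estimate the association of antidepressants with patient-reported outcomes but specifies no adjusted estimate, so the protocol's propensity framework is not carried through.

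*SAP*

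**What the plan says.** In the SAP's Analysis Tasks, the aim of Objective 6 is "To estimate the associations between antidepressant use (any vs. none) and patient reported outcomes (modified Rankin Scale", then EQ-5D-3L, PHQ-2, SIS-16 and Fatigue Severity Scale. Figure 6 (stacked bars of mRS by group) and Tables 6A-6G follow. The tables hold percentages, means with standard errors, and medians, by group and time point; an example is "Table 6A. EQ-5D-3L distribution by AD use at discharge, 3 month and 6 month". None has a column for a difference, odds ratio, confidence interval or adjusted value. Objectives 1 to 5 each have an Analysis paragraph; Objective 6 has none.

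Weighting is specified under Objective 2, with this reason: "Because patients who receive AD may differ from those who do not on important baseline and clinical characteristics". Its scope is also stated: "Following IPW, we will compare primary and secondary endpoints between treatment groups". The primary endpoint is "Home-time: Total number of days spent alive and outside of a hospital" (the definition goes on to other facilities), and the secondary endpoints are mortality and readmissions. No patient-reported outcome is on either list. The weighting is extended to SSRI vs other antidepressants for clinical outcomes, and to subgroups by repeating Tables 2 and 3.

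The protocol's Statistical Considerations adopt propensity methods in general, with balance judged by standardised differences, multivariable logistic regression for dichotomous outcomes (mRS is an example), multivariable linear regression for continuous ones, and GEE for clustering by hospital. They list no covariates.

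Objective 7 is built like Objective 6: "To estimate the associations between antidepressant use (SSRI vs. other) and patient reported outcomes (modified Rankin Scale" and the same scales, with matching by-group tables.

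**The concern.** The exposure is a prescription chosen by clinicians, and PHQ-2 and the EQ-5D anxiety/depression item measure the condition for which it is likely to be given. A raw comparison therefore mixes any drug effect with the reason for prescribing. Objective 2 recognises this for claims outcomes, but nothing in the SAP does so for patient-reported ones. Table 5A would display baseline imbalance in the prospective cohort without removing it.

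A reader can form a crude contrast from the group means and standard errors in Tables 6B, 6C and 6E-6G. With imbalance like that in the retrospective cohort, such a contrast could make antidepressants appear to worsen mood and quality of life when they do not. If adjustment is to be added, its covariates and outcomes should be fixed before results are seen.

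**Working it through.** **1. Is adjustment specified elsewhere in the SAP?** Three places could supply it.
- Objective 2 weights the primary and secondary endpoints, none of them patient-reported.
- The extensions of that weighting concern clinical outcomes and Tables 2 and 3.
- Objective 5 tabulates baseline characteristics and links no model to them.

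The Objective 2 tables do have unadjusted and adjusted columns; Tables 6A-6G do not.

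**2. Size of the documented imbalance.** Inputs are the counts under the SAP's Primary exposure variable (retrospective, 65+; prior use excludes missing values). Standardised difference = (p1 − p0) / √{[p1(1 − p1) + p0(1 − p0)] / 2}.
- Depression history: 3,309/7,593 = 43.58% vs 1,032/21,584 = 4.78%. Difference 38.8 points; 0.388/0.382 = 102%.
- Prior antidepressant: 5,678/7,514 = 75.57% vs 754/21,355 = 3.53%. Difference 72.0 points; 0.720/0.331 = 218%.
- SSRI vs other, depression history: 474/1,072 = 44.22% vs 193/446 = 43.27%; 1.9%.
- SSRI vs other, prior antidepressant: 800/1,062 = 75.33% vs 325/443 = 73.36%; 4.5%.

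The percentages agree with those printed in the SAP.

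**3. What this could do to a crude contrast (illustration only).** Assume no drug effect, the same imbalance in the prospective cohort, depression history as the only confounder, and a binary outcome such as PHQ-2 ≥ 3 that is g points more common with a depression history. The documents give no value for g. Raw difference = 0.388 × g:
- g = 10: 3.9 points
- g = 20: 7.8 points
- g = 30: 11.6 points

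**4. Precision cost of weighting.** Weight on prior antidepressant use alone, with the retrospective proportions.
- P(antidepressant | prior use) = 5,678/6,432 = 0.883. P(antidepressant | no prior use) = 1,836/22,437 = 0.082.
- Weights if treated: 1/0.883 = 1.13 (prior use) and 22,437/1,836 = 12.22 (none). If untreated: 6,432/754 = 8.53 and 22,437/20,601 = 1.09.
- Effective fraction = (mean w)² / mean(w²). Treated, with shares 75.57% and 24.43%: 3.84²/37.5 = 39.4%. Untreated, with shares 3.53% and 96.47%: 1.35²/3.71 = 49.2%.
- At N = 2,000 with 26.0% treated (520 vs 1,480), the variance factor is 1/520 + 1/1,480 = 0.00260 raw, and 1/(0.394 × 520) + 1/(0.492 × 1,480) = 0.00625 weighted. SE ratio = √(0.00625/0.00260) = 1.55.
- Restricting to patients naive to antidepressants leaves 24.43% of 520 = 127 and 96.47% of 1,480 = about 1,428. SE ratio = √[(1/127 + 1/1,428)/0.00260] = 1.82.

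**The case against.** The strongest reply is that the protocol already answers this: propensity methods, a balance check, multivariable regression with mRS named, and GEE. This stands in part. A reader might infer that PROSPER plans no adjustment at all for patient-reported outcomes, and the documents do not support that. The fault is narrower. The protocol speaks in general terms and names no covariates, and the SAP, where they would be fixed, omits them for Objective 6. Nor does the SAP call Tables 6A-6G unadjusted; that follows from the missing paragraph and columns.

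It is also tempting to quote a false-positive rate for the raw comparison. Tables 6A-6G contain no test or interval, so no planned test has such a rate, and any figure would rest on assumed outcome gaps and on a different cohort. The 3.9 to 11.6 points are likewise not a test against the protocol's 8% detectable difference, because the protocol does not say which outcome or scale that refers to.

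The tables have discharge columns, so baseline scores might seem to be available to separate prior depression from later effect. Side-by-side columns do not adjust anything, and the protocol's schedule lists the interview only at 3 and 6 months. Whether these scores will exist is unclear.

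Finally, Objective 6 could be read as descriptive. But its aim is to estimate associations, whereas the Analysis Tasks aims of Objectives 1, 3 and 5 are to describe, and the protocol's prospective power statement compares treated with untreated patients.

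**Conclusion.** The point holds as a gap between aim and analysis: Objective 6 promises an association, and the SAP specifies only by-group summaries. That conclusion rests on the text alone. The likely size of the confounding is conditional. The standardised differences of 102% and 218% are documented only for the retrospective 65+ cohort, the prospective cohort's imbalance is not reported, and the raw difference of 3.9 to 11.6 points needs the assumed outcome gaps as well.

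This should be fixed, but it does not reach the primary endpoint, home-time, which is covered by the Objective 2 analysis.

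Objective 7 is a lesser gap. A reader might infer that it is confounded to the same degree; the documents do not support that, since the SSRI and other-antidepressant groups are nearly balanced on the two reported factors (1.9% and 4.5%). Near balance on those two does not show balance on stroke severity or function.

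**What to change.** Add an Analysis paragraph to Objective 6 that applies the Objective 2 weighting to the patient-reported outcomes:
- **Covariates:** use those fixed at or before admission, from the SAP's Other variables: demographics, medical history including depression, and presentation items ("EMS transport, ambulatory status, initial NIHSS, prior antidepressant use"), plus hospital variables. State how discharge variables are treated and why. The Objective 2 list taken literally includes discharge antidepressants, which are the exposure, while ambulatory status at discharge could be a genuine confounder for mRS and SIS-16.
- **Checks and errors:** a weighted balance check and hospital-clustered robust standard errors.
- **Output:** add adjusted columns with 95% CIs: odds ratios for mRS (dichotomous as in the protocol, or state the change) and PHQ-2 ≥ 3; mean differences for EQ-5D index, EQ VAS, SIS-16 and Fatigue Severity Scale. Label Tables 6A-6G unadjusted.
- **Sensitivity:** antidepressant-naive patients only, a restriction Objective 3 already uses.
- **Baseline scores:** reconcile the discharge columns with the protocol's interview schedule before any baseline-score adjustment.

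For Objective 7, add the same adjusted estimates or reword the aim to describe.

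The change needs SAP text and model runs, but no new patients or visits: Table 5A already plans depression history, prior antidepressants and NIHSS for this cohort. The real cost is precision. With the 1.55 ratio, 26% treated and an assumed untreated rate of 15% to 46%, power for an 8-point difference at N = 2,000 falls from 88-97% raw to 53-70% weighted. At the combined N = 5,000, weighted power is 89-98%. More covariates and lost interviews would probably lower these figures.

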## EQ-5D-3L Health Profile

Table 6A. EQ-5D-3L distribution by AD use at discharge, 3 month and 6 month

EQ-5D-3L Dimension		AD (% Subjects)			Not on AD (% Subjects)		
		At discharge	3 month	6 month	At discharge	3 month	6 month
Mobility	Level 1						
	Level 2						
	Level 3						
Self-Care	Level 1						
	Level 2						
	Level 3						
Usual Activity	Level 1						
	Level 2						

	Level 3						
Pain/Discomfort	Level 1						
	Level 2						
	Level 3						
Anxiety/Depression	Level 1						
	Level 2						
	Level 3						

Table 6B. EQ-5D-3L index values

EQ-5D-3L index value	AD			Not on AD		
	At discharge	3 month	6 month	At discharge	3 month	6 month
Mean (Standard error)						
Median (25 th – 75 th percentile)						

Table 6C. EQ VAS

EQ VAS	AD			Not on AD		
	At discharge	3 month	6 month	At discharge	3 month	6 month
Mean (Standard error)						
Median (25 th – 75 th percentile)						

Table 6D. PHQ-2 Score distribution

PHQ-2 Score	AD (% Subjects)			Not on AD (% Subjects)		
	At discharge	3 month	6 month	At discharge	3 month	6 month
0						
1						
2						
3						
4						
5						
6						

Table 6E. PHQ-2 Score

PHQ-2 Score	AD			Not on AD		
	At discharge	3 month	6 month	At discharge	3 month	6 month
Mean (Standard error)						
Median (25 th – 75 th percentile)						
% Subjects >= 3						

Table 6F. Stroke Impact Scale-16

SIS-16	AD			Not on AD		
	At discharge	3 month	6 month	At discharge	3 month	6 month
Mean (Standard error)						
Median (25 – 75 percentile)						
Percent at floor (SIS16 = 0)						
Percent at Ceiling (SIS16 = 100)						

[figure not shown]
Table 6G. Fatigue Severity Scale

Fatigue Severity Scale	AD			Not on AD		
	At discharge	3 month	6 month	At discharge	3 month	6 month
Mean (Standard error)						
Median (25 th – 75 th percentile)						
% Subjects >= 36						

## 7. Objective 7

**Aim:** To estimate the associations between antidepressant use (SSRI vs. other) and patient reported outcomes (modified Rankin Scale, EQ-5D-3L Health Profile, PHQ-2 score, SIS-16 score and Fatigue Severity Scale score).

**Figure 7.** Grotta bar showing SSRI vs other AD use and mRS following ischemic stroke discharge.

## EQ-5D-3L Health Profile

Table 7A. EQ-5D-3L distribution by AD type use at discharge, 3 month and 6 month

EQ-5D-3L Dimension		SSRI (% Subjects)			Other type AD (% Subjects)		
		At discharge	3 month	6 month	At discharge	3 month	6 month
Mobility	Level 1						
	Level 2						
	Level 3						
Self-Care	Level 1						
	Level 2						
	Level 3						
Usual Activity	Level 1						
	Level 2						
	Level 3						
Pain/Discomfort	Level 1						

	Level 2						
	Level 3						
Anxiety/Depression	Level 1						
	Level 2						
	Level 3						

Table 7B. EQ-5D-3L index values

EQ-5D-3L index value	SSRI			Other AD		
	At discharge	3 month	6 month	At discharge	3 month	6 month
Mean (Standard error)						
Median (25 th – 75 th percentile)						

Table 7C. EQ VAS

EQ VAS	SSRI			Other AD		
	At discharge	3 month	6 month	At discharge	3 month	6 month
Mean (Standard error)						
Median (25 th – 75 th percentile)						

Table 7D. PHQ-2 Score distribution

PHQ-2 Score	SSRI (% Subjects)			Other AD (% Subjects)		
	At discharge	3 month	6 month	At discharge	3 month	6 month
0						
1						
2						
3						
4						
5						
6						

Table 7E. PHQ-2 Score

PHQ-2 Score	SSRI			Other AD		
	At discharge	3 month	6 month	At discharge	3 month	6 month
Mean (Standard error)						
Median (25 th – 75 th percentile)						
% Subjects >= 3						

Table 7F. Stroke Impact Scale-16

SIS-16	SSRI			Other AD		
	At discharge	3 month	6 month	At discharge	3 month	6 month
Mean (Standard error)						
Median (25 – 75 percentile)						
Percent at floor (SIS16 = 0)						
Percent at Ceiling (SIS16 = 100)						

Table 7G. Fatigue Severity Scale

Fatigue Severity Scale	SSRI			Other AD		
	At discharge	3 month	6 month	At discharge	3 month	6 month
Mean (Standard error)						
Median (25 th – 75 th percentile)						
% Subjects >= 36
